4.8. Analysis Populations

The Randomized population includes all subjects who are randomized.

The Safety population includes all subjects who receive any amount of study drug.

The PK population includes subjects who receive at least 1 dose of study drug and have at least 1 measurable PK concentration.

The PD population includes subjects who receive at least 1 dose of ticagrelor and have at least 1 measurable post dose LTA value.

5. Subject Disposition

Screen failures will be listed together with screening date and reason for failure.

Subject disposition data including screening date, randomization information, reasons for subjects excluded from the analysis populations, and study completion will be presented in data listings. The frequency and percentage of subjects who completed and discontinued from the study together with reason for premature withdrawal, and subjects who completed and discontinued the study drug together with reason for not completing the study drug will be summarized for the randomized subjects by treatment group and overall. Subjects included in each analysis population will be summarized for each treatment group and overall.

5.1. Protocol Deviations and Eligibility Criteria Deviations

Protocol deviations will be listed. Eligibility with regards to inclusion and exclusion criteria will be listed.

6. Demographics and Baseline Characteristics

6.1. Demographics

Demographic information will be presented in a listing and summarized in a table. Descriptive statistics will be calculated for age (years, calculated as the integer part of [date of informed consent - date of birth]/365.25), screening weight, height, and body mass index (BMI). Frequency counts and percentages will be tabulated for sex, race, and ethnicity. The summaries will be presented by treatment groups (as defined in [Section 4.1](#)) and overall for the Safety population.

6.2. Medical History

The medical history findings will be presented in a listing.

7. Treatments and Medications

7.1. Prior and Concomitant Medications

Information about prior medications taken by the subject within the 30 days before he or she provides informed consent will be recorded in the subject's eCRF.

Prior medications are defined as medications taken prior to the initiation of study drug. Concomitant medications are defined as medications that were taken on or after the initiation of study drug. A medication can be considered as both prior and concomitant if the medication is taken prior to the initiation of study drug and continued into the treatment period.

Prior and concomitant medications will be coded using the latest version of the World Health Organization Drug Dictionary (version March 2018 or later) and presented in a listing.

7.2. Medical and Surgical Procedures

Medical and surgical procedures will be presented in a listing.

7.3. Study Treatments

The dosing regimens of study drugs in each cohort are as follows:

- Cohort 1: single 30-minute IV infusion of 100 mg MEDI2452 (PB2452) or matching placebo in the morning on Day 1
- Cohort 2: single 30-minute IV infusion of 300 mg MEDI2452 (PB2452) or matching placebo in the morning on Day 1
- Cohort 3: single 30-minute IV infusion of 1000 mg MEDI2452 (PB2452) or matching placebo in the morning on Day 1
- Cohort 4: simultaneous with the 5th ticagrelor dose, a single 30-minute IV infusion of 1000 mg MEDI2452 (PB2452) or matching placebo on Day 1
- Cohort 5: simultaneous with the 5th ticagrelor dose, a single 30-minute IV infusion of 3000 mg MEDI2452 (PB2452) or matching placebo on Day 1
- Cohort 6: simultaneous with the 5th ticagrelor dose, a single 30-minute IV infusion of 9000 mg MEDI2452 (PB2452) or matching placebo on Day 1

- Cohort 7: 2 hours following the 5th ticagrelor dose, a single IV infusion of 18000 mg MEDI2452 (PB2452) or matching placebo on Day 1. The single IV infusion of 18000 mg MEDI2452 (PB2452) or matching placebo will be delivered as a 3000 mg loading dose (41.7 mL) in the first 5 minutes at a rate of 500 mL/hour, followed by a 15000 mg maintenance dose (208.3 mL) delivered over the remaining 7 hours and 55 minutes at a rate of 26.3 mL/hour. The final volume is 250 mL ([Memo Re: PB2452-PT-CL-0001 Cohort 7 Dosing Regimen](#)).
- Cohort 8: 2 hours following the 5th ticagrelor dose, a single IV infusion of 18000 mg MEDI2452 (PB2452) or matching placebo on Day 1. The single IV infusion of 18000 mg MEDI2452 (PB2452) or matching placebo will be delivered as a 6000 mg loading dose (83.3 mL) in the first 15 minutes at a rate of 333 mL/hour, followed by a 6000 mg dose (83.3 mL) over the next 3 hours at a rate of 27.7 mL/hour, and followed by a 6000 mg dose (83.4 mL) over the remaining 8 hours and 45 minutes at a rate of 9.53 mL/hour. The final volume is 250 mL ([Memo Re: PB2452-PT-CL-0001 Cohort 8 Dosing Regimen](#)).
- Cohorts 9 and 10: 2 hours following the 5th ticagrelor dose, a single IV infusion of 18000 mg MEDI2452 (PB2452) or matching placebo on Day 1. The single IV infusion of 18000 mg MEDI2452 (PB2452) or matching placebo will be delivered as a 6000 mg loading dose (83.3 mL) in the first 15 minutes at a rate of 333 mL/hour, followed by a 6000 mg dose (83.3 mL) over the next 4 hours at a rate of 20.8 mL/hour, and followed by a 6000 mg dose (83.4 mL) over the remaining 12 hours and 5 minutes at a rate of 6.9 mL/hour. The final volume is 250 mL ([Memo Re: PB2452-PT-CL-0001 Cohorts 9 and 10 Dosing Regimens](#)).

Study drug administration data will be presented in a listing.

8. Safety Analysis

Safety and tolerability will be assessed by monitoring and recording of AEs, clinical laboratory test results (hematology, coagulation, serum chemistry, and urinalysis), vital

sign measurements (systolic and diastolic blood pressures, oral body temperature, respiratory rate, and heart rate), ECG results, cardiac telemetry, and physical examination findings.

8.1. Adverse Events

An AE is defined as any untoward medical occurrence associated with the use of a drug in humans, whether or not considered drug-related.

A TEAE is defined as any event not present before exposure to study drug or any event already present that worsens in intensity or frequency after the exposure. For analysis purposes, TEAEs are the events with onset on or after initiation of study drug.

Adverse events will be coded using the Medical Dictionary for Regulatory Activities (MedDra), version 21.0 or higher, by system organ class (SOC) and preferred term (PT).

All summary tables except from the overall summary table will be based on TEAEs. The SOCs will be displayed in descending order of overall frequency and then alphabetically. The PTs will be displayed in descending order of overall frequency and then alphabetically within SOC. A subject with 2 or more AEs within the same level of summarization will be counted only once in that level using the most severe (for the severity table) or most related (for the relationship to study drug table) incident.

Summary tables will be presented by treatment groups as defined in [Section 4.1](#). Percentages will be based upon the number of subjects in the safety population overall and within each treatment group.

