3.5.4 Adverse Events

3.5.4.1 Adverse Event Definitions

The investigator is responsible for reporting all AEs that are observed or reported during the study, regardless of their relationship to study drug or their clinical significance. If there is any doubt as to whether a clinical observation is an AE, the event should be reported.

An AE is defined as any untoward medical occurrence associated with the use of a drug in humans, whether or not considered drug-related. Subjects will be instructed to contact the investigator at any time after randomization if any symptoms develop.

A TEAE is defined as any event not present before exposure to study drug (MEDI2452 [PB2452]) or any event already present that worsens in intensity or frequency after exposure.

A suspected adverse reaction is any AE for which there is a reasonable possibility that the study drug caused the AE. For the purposes of investigational new drug safety reporting, “reasonable possibility” means that there is evidence to suggest a causal relationship between the study drug and the AE. A suspected adverse reaction implies a lesser degree of certainty about causality than adverse reaction, which means any AE caused by a study drug.

An adverse reaction is any AE caused by a drug. Adverse reactions are a subset of all suspected adverse reactions for which there are reasons to conclude that the drug caused the event.

An AE or suspected adverse reaction is considered “unexpected” if it is not listed in the investigator brochure or at the specificity or severity that has been observed with the study drug being tested; or, if an investigator brochure is not required or available, is not consistent with the risk information described in the general investigational plan or elsewhere in the

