3.5.4.2 Eliciting and Documenting Adverse Events

The investigator is responsible for ensuring that all AEs and SAEs are recorded in the eCRF and reported to PhaseBio Pharmaceuticals, Inc. Adverse events will be assessed from the time of pretreatment dosing with ticagrelor on Day -2 until completion of all study procedures and EOS assessments (Day 28).

Subjects may spontaneously report and/or will be asked a standard question to elicit any medically related changes in their well-being. They will also be asked if they have used any new medications, or changed concomitant medication regimens (both prescription and over-the-counter medications).

In addition to subject observations, AEs will be documented from any data collected on the AE page of the eCRF (eg, laboratory values, physical examination findings, and ECG changes) or other documents that are relevant to subject safety.

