3.5.4.4 Assessment of Severity

The severity (or intensity) of an AE refers to the extent to which it affects the subject's daily activities and will be classified as mild, moderate, or severe using the following criteria:

- Mild: These events require minimal or no treatment and do not interfere with the subject's daily activities.
- Moderate: These events result in a low level of inconvenience or concern with the therapeutic measures. Moderate events may cause some interference with normal functioning.
- Severe: These events interrupt a subject's usual daily activity and may require systemic drug therapy or other treatment. Severe events are usually incapacitating.

Changes in the severity of an AE should be documented to allow an assessment of the duration of the event at each level of intensity to be performed. An AE characterized as intermittent requires documentation of onset and duration of each episode.

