2.3. Exploratory

The exploratory objective is to evaluate the effect of MEDI2452 (PB2452) on the PK profile of unbound ticagrelor and unbound AR-C124910XX plasma concentrations.

3. Investigational Plan

This is a Phase 1, first-in-human, randomized, double-blind, placebo-controlled, single ascending dose, sequential group study to evaluate the safety, tolerability, PK, and PD of MEDI2452 (PB2452) with and without ticagrelor pretreatment when administered to healthy male and female subjects. All references to study drug within this statistical analysis plan (SAP) apply to MEDI2452 (PB2452) or matching placebo.

This study will have up to 10 cohorts and up to a total of 68 subjects with either 4 or 8 subjects in each cohort. The starting dose of MEDI2452 (PB2452) will be 100 mg and the planned doses for subsequent cohorts are 300, 1000, 3000, 9000, and 18000 mg. Other intermediate doses may also be tested but will not exceed 1800 mg.

The study will consist of a screening period (Days -45 to -4), check-in/pretreatment (Day -3 to Day -1), an in-house treatment period (Days 1 through 3 [Cohorts 1 through 8] or 4 [Cohorts 9 and 10]), and follow-up visits (Days 4, 7, and 28 [+2 days]). Subjects will receive an IV dose of study drug on Day 1.

On Day 1, subjects who meet all the inclusion criteria and none of the exclusion criteria will be randomly assigned to receive MEDI2452 (PB2452) or placebo in a ratio of 3:1 in all treatment cohorts as described below and as summarized in [Table 3-1](#).

Table 3-1 Summary of Treatment per Cohort

Cohort	Pre-MEDI2452 (PB2452) ticagrelor dosing to steady state (180 mg + 90 mg bid for 5 doses total)	MEDI2452 (PB2452) Dose (mg)	Number of subjects MEDI2452 (PB2452):placebo
1		100	3:1
2		300	3:1
3		1000	3:1
4	180 mg + 90 mg bid	1000	6:2
5	180 mg + 90 mg bid	3000	6:2
6	180 mg + 90 mg bid	9000	6:2
7	180 mg + 90 mg bid	18000	6:2
8	180 mg + 90 mg bid	18000	6:2
9	180 mg + 90 mg bid	18000	3:1 or 6:2*
10	180 mg + 90 mg bid	18000	3:1 or 6:2*

Abbreviations: bid, twice daily.

*Initially the cohort size will be 4 subjects (3:1); if needed for confirmation of PK/PD an additional 4 subjects (3:1) will be randomized in that same cohort.

Cohorts 1 to 3:

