4.7. Handling of Missing Data

Subjects with missing data for some summary statistic will not be included in the calculation of that statistic but are eligible for inclusion in any other summary statistic for which they provide data. For the purpose of determining inclusion of AEs in treatment-emergent AE (TEAE) summary tables, incomplete or missing AE onset and end dates will be imputed as follows:

Incomplete or missing onset dates (where UK and UNK indicate unknown or missing day and month, respectively):

- UK-MMM-YYYY: If the month and year are different from the month and year of the dose of study drug, assume 01-MMM-YYYY. If the month and year are the same as the dose of study drug month and year, and the end date (after any imputation) is on or after the dose of study drug, then assume the date of the dose of study drug. If the month and year are the same as the dose of study drug month and year and the end date (after any imputation) is prior to the dose of study drug, then assume the end date for the onset date.
- DD-UNK-YYYY or UK-UNK-YYYY: If the year is different from the year of dose of study drug, assume DD-JAN-YYYY or 01-JAN-YYYY of the onset year, respectively. If the year is the same as the dose of study drug year, and the end date (after any imputation) is on or after the dose of study drug, then assume the date of the dose of study drug. If the year is the same as the dose of study drug, and the end date (after any imputation) is prior to the dose of study drug, then assume the end date for the onset date.
- Missing onset date: If the onset date is completely missing and the end date (after any imputation) is on or after the dose of study drug, then assume the date of the first dose of study drug. If the end date (after any imputation) is prior to the dose of study drug, then assume the end date for the onset date.

Incomplete or missing end dates (where UK and UNK indicate unknown or missing day and month respectively):

- UK-MMM-YYYY: Assume the last day of the month;
- DD-UNK-YYYY or UK-UNK-YYYY: Assume DD-DEC-YYYY or 31-DEC-YYYY, respectively;
- Missing end date: Assume 31-DEC-YYYY, where YYYY is the year of the dose of study drug.

An AE with missing onset time but with an onset date the same as the dosing date of study drug will be classified as treatment-emergent, unless the AE was reported pre-dose with the same or worse intensity or frequency.

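### The SAP's analysis rule for TEAEs uses onset alone, so a run-in event that worsens after the infusion but keeps its run-in onset fails the rule, although the SAP defines it as a TEAE

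*SAP*

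**What the plan says.** SAP section 8.1 gives two rules in adjacent sentences. The definition has two limbs, the second covering worsening once exposed: "A TEAE is defined as any event not present before exposure to study drug or any event already present that worsens in intensity or frequency". The next sentence is the one a programmer would code: "For analysis purposes, TEAEs are the events with onset on or after initiation of study drug".

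Protocol section 3.5.4.1 has the same two-limb definition, including "any event already present that worsens in intensity or frequency after exposure". SAP section 12, which lists changes to the planned analysis, does not mention a narrower TEAE rule.

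Two further statements fix the timing. SAP section 3 says "All references to study drug within this statistical analysis plan (SAP) apply to MEDI2452 (PB2452) or matching placebo", so ticagrelor does not start the TEAE clock. Protocol section 3.5.4.2 says "Adverse events will be assessed from the time of pretreatment dosing with ticagrelor on Day -2".

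On recording, protocol section 3.5.4.4 says "Changes in the severity of an AE should be documented" so that time spent at each intensity can be assessed, and it asks for the onset and duration of each episode of an intermittent event. SAP section 4.7 brings intensity into classification in one narrow case. An event dated on the dosing day with no onset time counts as treatment-emergent "unless the AE was reported pre-dose with the same or worse intensity or frequency".

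**The concern.** The definition and the analysis rule give different answers for one kind of event: one that begins during ticagrelor pretreatment and becomes worse after the infusion. This is the kind of event for which the worsening limb exists. Safety and tolerability is a primary objective (SAP section 2.1), and section 8.1 bases every adverse event summary table except the overall one on TEAEs. In the SAP's table list these are Tables 14.3.1.2 to 14.3.1.6: by system organ class and preferred term, by preferred term, by relationship to study drug, by relationship to ticagrelor, and by severity. A worsening that followed PB2452 could be absent from all five.

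The gap applies to any adverse event recorded before the infusion. It matters most in the ticagrelor cohorts, because there adverse events are collected for about two days of dosing before study drug starts.

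**Working it through.** The plan gives no figure to reproduce for this point. The check is a comparison of the two rules, then a count of the subjects to whom the difference can apply.

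**Length of the run-in.** SAP section 3 has a first ticagrelor dose on the morning of Day -2 and four more at 12-hour intervals, so the 5th dose falls 4 × 12 = 48 hours after the first. The infusion starts with the 5th dose in Cohorts 4 to 6 (48 hours) and 2 hours later in Cohorts 7 to 10 (50 hours). An event with onset in that window precedes study drug.

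**The two rules side by side.** Definition: onset on or after study drug, or worsened after exposure. Analysis rule: onset on or after study drug.

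| Event | Definition | Analysis rule |
|---|---|---|
| Run-in onset, worsens after infusion, one record with run-in onset | TEAE | not TEAE |
| Run-in onset, unchanged | not TEAE | not TEAE |
| Onset after infusion | TEAE | TEAE |
| Worsening entered as a new record with onset after infusion | TEAE | TEAE |

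The rules part only in the first row.

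**Subjects with a run-in (SAP Table 3-1).** Cohorts 4 to 8 have 8 subjects each (6 active, 2 placebo). Cohorts 9 and 10 have 4 each (3 active, 1 placebo), with a possible 4 more.

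- Both kept at 4: 5 × 8 + 2 × 4 = 48 subjects, of whom 5 × 6 + 2 × 3 = 36 are active.
- Both expanded to 8: 5 × 8 + 2 × 8 = 56 subjects, of whom 5 × 6 + 2 × 6 = 42 are active.
- Adding Cohorts 1 to 3 (3 × 4 = 12) gives totals of 60 and 68. The second matches the SAP's maximum of 68.

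**Weight of one subject.** One reclassified subject moves an incidence cell by 1/6 = 16.7 percentage points in an active group of 6, and by 1/3 = 33.3 points in a group of 3. A ticagrelor group has 3 active subjects only if Cohort 9 or Cohort 10 stays at 4.

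**Reach in the overall summary (SAP section 8.1.1).** Five of the nine lines are TEAE or treatment-emergent counts: any TEAE, related, severe, severe and related, and treatment-emergent related SAE. The other four (any SAE, any event leading to early study discontinuation, any DLT, any death) are not worded as TEAE-only.

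**The case against.** The strongest reply is that sites may enter each worsening as a new record with its own onset. The onset rule would then capture it, and the two sentences would agree in practice. Some of the text leans that way. Assessing duration at each intensity requires dates for each level, and episodes of an intermittent event have their own onsets. The section 4.7 comparison with a pre-dose report also makes sense if one event can have a pre-dose report and a later dated record. In addition, the SAP reflects protocol amendment 5 of 03 August 2018, while the protocol supplied is dated 01 February 2018, so the recording instructions in force may differ from those cited here.

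This part stands: the loss is conditional. A reader might infer that every worsened run-in event is certain to be lost, but the documents do not support that, because they neither require nor exclude a new dated record. A reader might also take section 4.7 as proof that the SAP's rules contradict each other. It is compatible with a new-record convention, so it shows only that intensity was meant to matter.

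The reply does not remove the conflict. Neither document states the convention. Protocol section 3.5.4.3 requires a new entry when a condition present at screening deteriorates, but it says nothing of the kind for an event that begins in the run-in.

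The effect is also bounded. All adverse events are listed and the safety summaries are descriptive. DLTs come from the safety review committee's own spreadsheet after review of all adverse events (SAP section 8.1.6). One DLT limb uses the term TEAE, but the committee makes that determination and the analysis flag does not.

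**Conclusion.** Wrong as written. The analysis rule omits a limb that both the SAP and the protocol include in the TEAE definition. Applied literally, it gives a wrong TEAE count whenever an event from the run-in worsens after the infusion and stays on its run-in record. The conclusion rests on the wording of SAP section 8.1, the SAP's meaning of study drug, and collection from Day -2. The consequence also depends on the recording convention, which the documents leave open.

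The exposed group is 48 to 56 subjects, including 12 to 14 on placebo (48 − 36 and 56 − 42). A reader may want an expected number of lost events. The documents give no rate for run-in events or for worsening, so none can be derived. Nor should the 56 be paired with the 33.3-point shift: 56 requires both late cohorts at 8, and every ticagrelor active group then has 6 subjects, where the shift is 16.7 points.

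The events would not vanish from the report. They would be missing from the TEAE tables and five lines of the overall summary, but they would remain in the listing and, where they qualify, in the other four lines.

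**What to change.** Replace the analysis sentence in SAP section 8.1 with: *For analysis, a TEAE is an event with onset on or after initiation of study drug, or an event with earlier onset that worsens in intensity or frequency on or after initiation of study drug.* Derive worsening from the dated severity changes that protocol section 3.5.4.4 asks to be documented. If the database instead opens a new record at each worsening, say so and state that the new record's onset date and time is used.

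Before choosing, confirm what the database holds. Protocol section 3.5.4.3 lists severity and time of onset among the items collected but no frequency item, so worsening in frequency may have to come from the recorded episodes of intermittent events.

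The cost is one sentence and one extra derivation, with no new data collection if severity changes are recorded as the protocol asks. TEAE counts may rise slightly.
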